#### 4.4.4 Medical history

Medical history will be coded using Medical Dictionary for Regulatory Activities (MedDRA) dictionary version 27.0 or higher and tabulated by system organ class (SOC), preferred term (PT). Subjects with multiple medical histories in the same SOC or PT are counted only once for the respective SOC or PT.

Summaries are ordered in decreasing frequencies order of SOC and then, within an SOC, in decreasing frequencies by PT. If the frequencies tie, an alphabetic order will be applied.

All medical history will be listed by subject number.

#### 4.4.5 Baseline Disease Characteristics

Duration of AD disease and baseline atopic dermatitis severity will be summarized descriptively.

Duration of AD disease (months) = (date of first dose - date of first diagnosis + 1)/30.4375, rounded to the one decimal place.

Baseline Eczema Area and Severity Index (EASI) score will be summarized descriptively.

Baseline Global Assessment of Disease Severity (IGA) score will be tabulated, and the subject number and percentage for the score will be presented.

Baseline Peak Pruritus Numerical Rating Scale (PP-NRS) score will be summarized descriptively. The baseline PP-NRS score is based on the average of daily PP-NRS

scores for the 7 days immediately preceding Day 1. In order to calculate an average for the score, the subject must have completed the diary for a minimum of 4 days during the previous 7 days.

Baseline conjunctivitis assessment is defined as the assessment on Day 1. The percentage of subjects with/without conjunctivitis at baseline will be tabulated.

Baseline total Body Surface Area (BSA) affected by AD will be summarized descriptively.

Baseline disease characteristics will be listed by subject number.

#### 4.5 Prior and Concomitant Medications

Prior and concomitant drug name will be coded using World Health Organization Drug (WHODrug) dictionary version Global B3 March 1, 2023 or higher and will be summarized by Anatomical Therapeutic Classification (ATC) therapeutic group (i.e., ATCII), Preferred Term Title (PTT) in safety analysis set. At each level of summarization, frequency and percentage of subjects will be displayed and a subject is counted once if he/she reports one or more medications at that level.

Prior medications are defined as medications that stopped before the date and time of the first dose; concomitant medications are defined as medications that are ongoing at the first dose or start after the first dose. Medications with missing start and/or stop dates will be imputed to determining whether it is concomitant. If it is impossible to determine the prior or concomitant status, it will be summarized as concomitant medications.

A listing of all prior and concomitant medications will be provided by subject number.

#### 4.6 Prior and Concomitant Non-Medication Therapy

Prior and concomitant non-drug treatment will be coded using Medical Dictionary for Regulatory Activities (MedDRA) dictionary version 27.0 or higher and tabulated by SOC, PT in safety analysis set.

A listing of all prior and concomitant non-medication therapy will be provided.

#### 4.7 Efficacy Analysis

Efficacy analysis will be summarized in efficacy analysis set. As a sensitivity analysis, the per protocol population will also be assessed.

#### 4.7.1 Eczema Area and Severity Index (EASI)

The EASI score is a composite index that measures the severity of AD based on the average intensity of four clinical signs (erythema, edema/papulation, excoriations, and lichenification) at four body areas (head, neck, upper extremities, and trunk and lower extremities), and the percentage of affected area for each of the four body areas.

The baseline for EASI is defined as the score measured prior to dosing on Day 1.

Measured values, changes from baseline and percent change from baseline in EASI score will be summarized descriptively on scheduled visit.

The primary efficacy endpoint is the proportion of subjects with EASI75 (a 75% reduction in the EASI score) at 2 weeks after last dose at Week 24. The exploratory endpoints include the proportion of subjects achieving EASI90 at Weeks 26 (2 weeks after last dose at Week 24), the proportion of patients with EASI50 at Week 26 (2 weeks after last dose at Week 24). The corresponding 95% two-sided confidence intervals (CIs) will be calculated using the exact binomial distribution and presented for EASI75, EASI90, and EASI50.

For primary analysis, the percent change from baseline in EASI score, EASI50, EASI75, EASI90 in the EASI score will be calculated with observed data. If the subject has missing value for EASI at scheduled visit, the subject will be excluded from the calculation of proportion at specify visit.

Mean (±standard deviation) of the percent change from baseline in EASI score with observed data will be plotted at scheduled visit.

For sensitivity analysis, the missing value will also be imputed with last observation carried forward (LOCF) method. The imputed data for the percent change from baseline in EASI score will be summarized descriptively on scheduled visit. The proportion of subjects with EASI50, EASI75 and EASI90 at 2 weeks after last dose at Week 26 will also be calculated with imputed data.

A listing of all EASI score will be provided by subject number.

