6 STUDY OBJECTIVES AND ENDPOINTS

Table 5. Objectives and Endpoints in BSI-045B-002 Study

Objectives	Endpoints	
Primary		
Primary Efficacy Objective:	Primary Efficacy Endpoint:	
To evaluate the efficacy of BSI-045B in patients with moderate to severe atopic dermatitis (AD)	Proportion of patients with ≥Eczema Area and Severity Index (EASI)75 at Week 26 (2 weeks after last dose at Week 24)	
Primary Safety Objective:	Primary Safety Endpoint:	
To evaluate the safety and tolerability of BSI-045B in patients with moderate to severe AD	Safety and tolerability as evidenced by the incidence of adverse events (AEs), anti-BSI-045B antidrug antibody (ADA) formation, clinical laboratory evaluations, 12-lead electrocardiography (ECGs), vital signs, and physical examinations. The relationships between study drugs and AEs will be evaluated by the Investigators.	
Secondary		
To evaluate the pharmacokinetics (PK) of BSI-045B	Pharmacokinetics listings will be provided. PK parameters might be estimated through compartmental modeling. Additionally, the PK/Efficacy relationship might be explored.	
To evaluate the immunogenicity of BSI-045B	Anti-BSI-045B ADA during and post BSI-045B treatment	
Exploratory		
To assess additional efficacy and safety outcomes of BSI- 045B	Proportion of patients with EASI90 at Week 26 (2 weeks after last dose at Week 24)	
	 Proportion of patients with EASI50 at Week 26 (2 weeks after last dose at Week 24) 	
	➤ Percent change from baseline in EASI at each visit	
	➤ Proportion of patients achieving Investigator's Global Assessment (IGA) 0 or 1 at 26 (2 weeks after last dose at Week 24)	
	 Percent changes in PP-NRS scores at Week 26 (2 weeks after last dose at Week 24) 	
	 Proportion of patients achieving Facial IGA 0/1 at Week 26 (2 weeks after last dose at Week 24) 	
	> Occurrence of conjunctivitis	

V4.0_8 Jul 2024 Page 38 of 68

Objectives	Endpoints
To evaluate the PD biomarkers of BSI-045B	Serum levels of thymus and activation regulated chemokine/C-C chemokine ligand 17 (TARC/CCL-17), periostin, and IgE during and post BSI-045B treatment

AD = atopic dermatitis; ADA = antidrug antibody; AE = adverse event; CCL-17 = C-C chemokine ligand 17; EASI = Eczema Area and Severity Index; ECG = electrocardiography; IGA = Investigator's Global Assessment; IgE = immunoglobulin E; ; PD = pharmacodynamic; PK = pharmacokinetic; PP-NRS = Peak Pruritus Numerical Rating Scale; TARC = thymus and activation regulated chemokine

V4.0_8 Jul 2024 Page 39 of 68

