7.9.3 Efficacy

Patients will be assessed to determine an EASI score at Screening, prior to dosing on Day 1 (baseline), at subsequent visits, and at the time of early withdrawal from the study.

The EASI score is a composite index that measures the severity of AD based on the average intensity of four clinical signs (erythema, edema/papulation, excoriations, and lichenification) at four body areas (head, neck, upper extremities, and trunk and lower extremities), and the percentage of affected area for each of the four body areas (Hanifin and Rajka, 1980). The primary efficacy endpoint is the proportion of patients with ≥EASI75 at Week 26 (2 weeks after last dose at Week 24).

The IGA and facial IGA require the Investigator to rate the severity of AD on a scale from 0 (clear) to 4 (severe).

The assessment tool for itching is the PP-NRS, on which the patient rates the maximum severity of the itch from AD on a scale from 0 (no itch) to 10 (worst itch imaginable) over a

V4.0_8 Jul 2024 Page 43 of 68

24-hour period. The baseline PP-NRS score is based on the average of daily PP-NRS scores for the 7 days immediately preceding Day 1. Patients will complete the rating scale daily using the patient diary beginning on Day -8, throughout the last study visit, and at the time of early withdrawal from the study. In order to calculate an average for the score, the patient must have completed the diary for a minimum of 4 days during the previous 7 days.

Exploratory efficacy and safety assessments will include the following. At each visit, the percentage of patients who achieve 50%, 75%, and 90% improvement in the EASI score from Day 1) and the change in EASI score from Day 1 will be calculated. Detailed analysis of all exploratory endpoint is described in the Statistical Analysis Plan (SAP).

- Proportion of patients with EASI90 at Week 26 (2 weeks after last dose at Week 24)
- Proportion of patients with EASI50 at Week 26 (2 weeks after last dose at Week 24)
- Percent change from baseline in EASI at each visit
- Proportion of patients achieving IGA 0 or 1 Week 26 (2 weeks after last dose at Week 24)
- Percent changes in PP-NRS scores at Week 26 (2 weeks after last dose at Week 24)
- Proportion of patients achieving Facial IGA 0/1 at Week 26 (2 weeks after last dose at Week 24)
- Occurrence of conjunctivitis

7.9.4 *Safety*

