11 STATISTICAL METHODS

11.1 Sample Size

With a minimum sample size of 20 patients, the maximum one-sided 95% confidence interval width for the proportion achieving EASI75 equals 21%.

With a maximum sample size of 24 patients, the maximum one-sided 95% confidence interval width for the proportion achieving EASI75 equals 19%.

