11.2 Statistical Approach

Statistical analyses will be descriptive in nature, with frequencies and percentages generated for categorical variables and mean, standard deviation, median, minimum, and maximum values generated for continuous variables. Exact one-sided 95% confidence intervals will be generated for primary and select secondary efficacy endpoints based on proportions.

Additional details regarding the statistical analyses will be presented in the Statistical Analysis Plan.

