# 2.3 Sample Size

With a minimum sample size of 20 patients, the maximum one-sided 95% confidence interval width for the proportion achieving EASI75 equals 21%.

With a maximum sample size of 24 patients, the maximum one-sided 95% confidence interval width for the proportion achieving EASI75 equals 19%.

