# 4. Statistical Analysis

# 4.1 General Considerations for Statistical Analysis

#### 4.1.1 General Rules

No statistical hypothesis testing or inferential analyses are planned. The general analytical approach for all endpoints will be descriptive in nature.

Continuous variables (such as age) will be summarized with the observed number, mean, median, standard deviation, minimum, and maximum; categorical variables will be summarized with frequency and percentage of each category.

Unless otherwise specified, in summary tables of continuous variables, the minimum and maximum values will be displayed to the same number of decimal places as the raw data; the mean, median, and percentiles will be presented to 1 extra decimal place compared to the raw data; and the standard deviation will be displayed to 2 extra decimal places compared to the raw data. The maximum number of decimal places is 3

and values will be truncated to 3 decimal places in situations where there are more than 3 decimal places. Frequency tabulations will be presented by number and percentage, where the percentage is presented in parenthesis to 1 decimal place.

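### The protocol specifies a one-sided exact 95% interval for the primary EASI75 proportion, the SAP reports a two-sided one, and the stated precision (21%/19%) fits only the first

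*SAP*

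**What the plan says.** Protocol 11.2, repeated in the synopsis under Statistical Methods, sets the interval: "Exact one-sided 95% confidence intervals will be generated for primary and select secondary efficacy endpoints based on proportions". It does not say whether the limit is a lower or an upper one.

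SAP 4.7.1 specifies something else for the same endpoint: "The corresponding 95% two-sided confidence intervals (CIs) will be calculated using the exact binomial distribution and presented for EASI75, EASI90, and EASI50". The SAP (V1.0, 13 September 2024) is later than the protocol (V4.0, 8 July 2024) and does not mention the change.

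The sample size rationale rests on precision alone. SAP 2.3 says that with 20 patients "the maximum one-sided 95% confidence interval width for the proportion achieving EASI75 equals 21" per cent. Protocol 11.1 says that with 24 patients "the maximum one-sided 95% confidence interval width for the proportion achieving EASI75 equals 19" per cent. Both sections and the synopsis carry both figures, and none of them defines width or gives a two-sided figure.

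Two further statements limit the scope. The secondary objectives in protocol Table 5 are pharmacokinetics ("To evaluate the pharmacokinetics (PK) of BSI-045B") and immunogenicity. EASI50, EASI90, IGA and facial IGA are listed in protocol 7.9.3 under "Exploratory efficacy and safety assessments will include the following".

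**The concern.** The two governing documents prescribe different intervals for the only primary efficacy endpoint, so a report that follows the SAP departs from the protocol without explanation. The SAP is also at odds with itself, because the interval whose precision is described in section 2.3 is never produced in section 4.7.1. Precision is the only justification given for 20 to 24 patients, so it should describe the interval that will be reported. The study is open-label, and an unexplained change of sidedness could later look as if it had been chosen with the results in view.

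**Working it through.** **Inputs.** n = 20 and 24 (protocol 11.1, SAP 2.3). One-sided 95% (protocol 11.2): α = 0.05 in one tail. Two-sided 95% (SAP 4.7.1): α = 0.025 in each tail. Exact binomial (Clopper-Pearson) limits for x responders out of n:

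- lower limit L(x) = the α quantile of Beta(x, n − x + 1), with L(0) = 0
- upper limit U(x) = the 1 − α quantile of Beta(x + 1, n − x), with U(n) = 1
- D = the largest value, over x = 0 to n, of x/n − L(x) or U(x) − x/n

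**Step 1: reproduce the stated figures (α = 0.05).**

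- n = 20: maximum at x = 13 (or 7). 0.6500 − 0.4420 = 0.2080, stated as 21%.
- n = 24: maximum at x = 16 (or 8). 0.6667 − 0.4786 = 0.1881, stated as 19%.

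The figures are therefore right as an estimate-to-limit distance. A Wald half-width with continuity correction (20.9% and 18.9%) also rounds to them and is a distance of the same kind. They are not the literal length of a one-sided interval: at 10/20 the lower limit is 30.2%, and the length up to 100% is 69.8%.

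**Step 2: same measure for the SAP's interval (α = 0.025 per tail).**

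- n = 20: maximum at x = 14 (or 6). 0.7000 − 0.4572 = 0.2428.
- n = 24: maximum at x = 16 (or 8). 0.6667 − 0.4468 = 0.2199.

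| | n = 20 | n = 24 |
|---|---|---|
| Stated | 21% | 19% |
| One-sided 95%, maximum distance | 20.8% | 18.8% |
| Two-sided 95%, maximum distance | 24.3% | 22.0% |
| Gap | 3.5 points | 3.2 points |
| Two-sided 95%, maximum full width | 45.6% (x = 10) | 41.8% (x = 12) |

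The two-sided figure at the largest planned n (22.0%) is worse than the stated figure at the smallest (21%). No sample size from 20 to 24 gives the reported interval the stated precision.

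**Step 3: effect on a reported limit.**

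- 10/20: one-sided lower limit 30.2%; two-sided interval 27.2% to 72.8%.
- 12/24: one-sided lower limit 31.9%; two-sided interval 29.1% to 70.9%.
- Over x = 1 to n, the two-sided lower limit lies below the one-sided one by 0.1 to 3.6 points (n = 20) or 0.1 to 3.2 points (n = 24).

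**Step 4: the denominator.** All these figures need 20 to 24 observed Week 26 scores. Under SAP 4.7.1, a patient with a missing score is left out: "the subject will be excluded from the calculation of proportion at specify visit". Protocol 7.3 replaces only patients who do not complete five doses, and the fifth scheduled dose is at Week 6. Follow-up ends 12 weeks after the last dose: Week 14 + 12 = Week 26, but Week 12 + 12 = Week 24. A patient last dosed at Weeks 6 to 12 with no missed doses is therefore neither replaced nor scheduled for a Week 26 visit. If, for illustration, 18 patients were observed, the maximum two-sided distance would be 25.7%.

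**The case against.** The conflict and the arithmetic are not in dispute; the argument is about weight. SAP 4.1.1 says "No statistical hypothesis testing or inferential analyses are planned", and neither document has a null rate, success threshold, go/no-go rule or target precision. The SAP's change is in the cautious direction, since its lower limit is always below the protocol's when there is at least one responder. SAP 2.3 labels its figures one-sided and they are correct as such. The gap of about 3 points is close to the worst case; at 4/20 the lower limits differ by only 1.4 points (7.1% against 5.7%). All of this stands, and it is why the point is not more serious.

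It does not remove the point. Protocol 11.2 leaves additional details to the SAP, but a change of sidedness already fixed in the protocol is more than a detail. A correct statement about an interval that will not be reported is not a precision statement for the one that will.

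It can also be argued that the protocol's reference to select secondary efficacy endpoints was meant to reach EASI50, EASI90 and IGA. Table 5 contains no secondary efficacy endpoint and classes these as exploratory, so as written their two-sided intervals contradict nothing. Finally, the denominator issue applies under either interval. It is noted here only because it bears on the same precision statement.

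**Conclusion.** The inconsistency is real and confined to EASI75. Protocol 11.2 and the synopsis require a one-sided exact 95% interval, SAP 4.7.1 reports a two-sided one, and SAP 2.3 describes only the former. On the estimate-to-limit measure, the reported interval has a maximum distance of 24.3% (n = 20) or 22.0% (n = 24), against the stated 21% and 19%. This rests on Clopper-Pearson limits, on reading width as the distance from estimate to limit (which reproduces the stated figures), and on 20 to 24 observed scores. No estimate or decision changes, so this is a correction that should be made rather than a threat to the trial's result.

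**What to change.** Choose one of two routes, for EASI75 only.

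1. **Keep the two-sided interval.** Restate SAP 2.3 as a maximum estimate-to-limit distance of 24% (n = 20) and 22% (n = 24), define width, and record in the SAP that this departs from protocol 11.2. Align protocol 11.1, 11.2 and the synopsis at the next amendment. If full widths (46% and 42%) are also given, label them as a different quantity. Cost: a SAP edit now, protocol edits that need Sponsor and IRB approval (protocol 12.5), and a stated precision about 3 points less favourable.
2. **Change the SAP alone.** In 4.7.1, report the protocol's exact one-sided 95% limit for EASI75 beside the two-sided interval, name the bound, and say which one is protocol-specified. In 2.3, say that 21% and 19% are estimate-to-limit distances for the one-sided limit. Cost: no amendment, but two intervals for one endpoint.

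Under either route, add one line to SAP 2.3 that the figures assume 20 to 24 patients with an observed Week 26 EASI. Leave SAP 4.7.2 and 4.7.4 unchanged. No extra patients or visits are needed.

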7.11 Criteria for Early Discontinuation of Study Drug

A patient has the right to withdraw from treatment at any time at his/her request and this decision will not affect the treatment provided by clinicians or research institutions in the future. Moreover, the patients may be withdrawn at any time at the discretion of the Investigators for safety, behavioral, compliance, or administrative reasons. When medically feasible, the Medical Monitor should be consulted prior to study drug discontinuation. Study drug treatment will be permanently discontinued if one of the following criteria applies:

- Withdrawal of consent
- Patient or guardian requests to discontinue the study drug
- Start of new anti-AD treatment
- Lost to follow-up
- Death
- Intolerable safety issues

V4.0_8 Jul 2024 Page 47 of 68

• AE, abnormal laboratory tests, or other medical condition (including pregnancy) occurred, and the Investigator judges that the study drug should be terminated based on the best interests of the patient

- Major noncompliance with the study protocol and in the Investigator's judgment, treatment should be discontinued
- Other conditions that the Investigator considers inappropriate for continue treatment
- Study terminated by the Sponsor

If a patient withdraws from study treatment after receiving study treatment, a safety examination is required within 7 days after the patient's withdrawal. Additional follow-up assessments should be completed.

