#### 4.1.4 Visit Window

The nominal visit as defined in protocol and recorded on the Case Report Form (CRF) will be used in the statistical analyses unless other specified. Regarding efficacy endpoints, the analysis visit during follow-up period will be dynamically derived. For instance, if the subject finished the last dosing visit at Week 14, the first follow-up visit (i.e. FU1) will be set as the first visit after Week 14 (i.e. Week16) and subsequent follow-up visits will be derived accordingly as Week18, Week20, Week 22, Week24, and Week 26. Unscheduled data will not be windowed into planned analysis visits for summary tables but will be included in overall post-baseline summaries, such as worst or last values.

In addition, unscheduled data will be listed and may be plotted in figures based on study days.

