# 4.7.2 Investigator's Global Assessment of Disease Severity (IGA)

The IGA requires the investigator to rate the severity of AD on a scale from 0 (clear) to 4 (severe).

The baseline for IGA is defined as the score measured on Day 1.

Proportion of subjects achieving an IGA response (IGA = 0 [clear] or IGA = 1 [almost clear] on a scale of 0–4, where 4 represents severe atopic dermatitis) at 2 weeks after last dose at Week 24 with observed data will be presented. If the subject has missing value for IGA at scheduled visit, the subject will be excluded from the calculation of proportion at specify visit. The corresponding 95% two-sided confidence intervals (CI), calculated using the exact binomial distribution, will also be presented.

A listing of all IGA result will be provided by subject number.

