#### 4.7.4 Facial IGA Assessment

Facial IGA assessment will be summarized with the same method of Investigator's Global Assessment (IGA).

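### No rule sets aside EASI or IGA values recorded after a switch to another AD therapy, so a late switcher can count as a Week 26 responder to BSI-045B monotherapy

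*SAP*

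**What the plan says.** SAP 4.7.1 gives the primary rule for the EASI responder endpoints: "EASI50, EASI75, EASI90 in the EASI score will be calculated with observed data". The only patients set aside are those without a value: "If the subject has missing value for EASI at scheduled visit, the subject will be excluded from the calculation of proportion at specify visit". The EASI sensitivity analysis adds that "the missing value will also be imputed with last observation carried forward (LOCF) method".

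SAP 4.7.2 repeats the exclusion for IGA 0/1: "If the subject has missing value for IGA at scheduled visit, the subject will be excluded from the calculation of proportion at specify visit". SAP 4.7.4 extends it: "Facial IGA assessment will be summarized with the same method of" IGA. No LOCF analysis is stated for either IGA endpoint.

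Protocol 7.11 lists "Start of new anti-AD treatment" among the reasons for stopping study drug permanently, and then says "Additional follow-up assessments should be completed". Section 7.12 does not list new treatment as a reason for leaving the study. Table 2 schedules EASI, IGA and facial IGA at FU1 to FU6.

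SAP 4.1.4 places those visits on the study calendar for the efficacy endpoints. In its example the last dose is at Week 14, FU1 becomes Week 16, and "subsequent follow-up visits will be derived accordingly as Week18, Week20, Week 22, Week24, and Week 26". Protocol 9.4 allows no rescue medication. Neither document says how a value recorded after the start of another AD therapy is analysed.

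**The concern.** The protocol foresees that some patients will stop BSI-045B for another AD treatment and asks for them to be followed. The SAP then turns their follow-up visits into study weeks and analyses whatever is observed. A patient who abandons BSI-045B at Week 14, starts another therapy and clears on it can therefore enter the primary numerator as a success of BSI-045B.

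The objective is efficacy as monotherapy. There is one unblinded arm, so no control group would show that a response came from another drug. Protocol 5.4 says the findings will be used to design Phase 2b, and the Week 26 EASI75 proportion is the primary efficacy result.

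**Working it through.** **The plan's own figure, for scale.** SAP 2.3 and Protocol 11.1 give a maximum one-sided 95% interval width of 21% at n=20 and 19% at n=24. The largest distance from estimate to exact (Clopper-Pearson) limit, over all response counts, is 20.8% and 18.8%, so the stated figures reproduce.

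**Which patients have a Week 26 value.** Inputs: 14 planned doses, 4 weekly (Weeks 1 to 4) and 10 two-weekly (Weeks 6 to 24), from SAP 4.8.1; six follow-up visits two weeks apart, from Table 2; relabelling from SAP 4.1.4. FU6 falls at last dose week + 12. Week 26 is visit FU k with k = (26 − last dose week)/2, which exists only if k ≤ 6.

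| Last dose | Doses given | FU6 at | Visit used as Week 26 | Weeks since last dose |
|---|---|---|---|---|
| Week 6 | 5 | Week 18 | none | – |
| Week 8 | 6 | Week 20 | none | – |
| Week 10 | 7 | Week 22 | none | – |
| Week 12 | 8 | Week 24 | none | – |
| Week 14 | 9 | Week 26 | FU6 | 12 |
| Week 16 | 10 | Week 28 | FU5 | 10 |
| Week 18 | 11 | Week 30 | FU4 | 8 |
| Week 20 | 12 | Week 32 | FU3 | 6 |
| Week 22 | 13 | Week 34 | FU2 | 4 |
| Week 24 | 14 | Week 36 | FU1 | 2 |

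The dividing line is a last dose at Week 14. A patient with all 14 doses who starts new therapy before FU1 is also counted as observed. Patients with 5 to 8 doses are not replaced under Protocol 7.3.

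**How much BSI-045B remains.** With the half-life of about 25 days in Protocol 5.2.3.4, and ignoring absorption, the fraction left at Week 26 is 0.5^(days/25). That is 0.5^(84/25) = 9.7% for a last dose at Week 14 and 0.5^(28/25) = 46.0% at Week 22. This bears on attribution only and does not enter the response figures.

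**Late switcher counted as responder.** With r other responders, the change is (r + 1)/n − r/n = 1/n: 1/20 = 5.0 points, 1/24 = 4.2 points. For a patient who would have responded anyway it is zero.

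**Early switcher without a Week 26 value.** Assume, for illustration, two non-responders with last dose at Week 6 to 12.
- Observed data: 10/18 = 55.6% against 10/20 = 50.0% (+5.6 points); 12/22 = 54.5% against 12/24 = 50.0% (+4.5 points).
- LOCF, if both last EASI values are non-responses: 10/20 and 12/24, so the gap closes.
- LOCF, if one of the two has a post-switch response carried forward: 11/20 = 55.0% and 13/24 = 54.2%.

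**One of each (assumed), split by cause.**
- n=20: 10/19 = 52.6% against 9/20 = 45.0%, +7.6 points. The late switcher supplies 10/20 − 9/20 = 5.0; the lost denominator supplies the other 2.6.
- n=24: 12/23 = 52.2% against 11/24 = 45.8%, +6.3 points. The late switcher supplies 12/24 − 11/24 = 4.2; the lost denominator supplies about 2.2.

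**The case against.** The text can be read less firmly. Protocol 7.11 requires a safety examination and then further assessments, without naming EASI or the FU1 to FU6 schedule. Table 2 gives patients who stop treatment an early-withdrawal visit within 7 days. Section 7.12 lets the investigator withdraw a patient for serious deviation or other reasons, and 11.3.2 allows important deviations to lead to removal from the analysis. The endpoint is defined as two weeks after a Week 24 dose, which a Week 14 stopper never received. Part of this stands: a late switcher who skips follow-up has no Week 26 value and leaves the denominator. But the worked example in SAP 4.1.4 is exactly a Week 14 stopper with visits mapped through to Week 26, so for patients who are followed the SAP does count them.

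The per-protocol analysis might remove switchers. It is a sensitivity analysis, does not name new AD therapy, depends on sponsor and investigator classification, and would drop these patients rather than count them as failures.

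A reader might infer that the loss of early switchers from the denominator is part of the same gap. It is not specific to switching: anyone with a last dose at Week 12 or earlier is lost, whatever the reason. A reader might also infer that no planned analysis brings them back. For EASI, LOCF does, and it scores them as failures when their last EASI is a non-response. That relief is absent for IGA and facial IGA, and for EASI it fails if the carried value was recorded after the switch.

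Finally, one switcher is worth 4 to 5 points against an interval width of 19 to 21 points, in a descriptive study with no hypothesis test. That limits the weight of the point; it does not make the counting rule right.

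**Conclusion.** The point holds for late switchers. The observed-data rule, the relabelling of follow-up visits and continued follow-up after a switch together score a response on another AD therapy as a Week 26 EASI75, IGA 0/1 or facial IGA 0/1 response to BSI-045B monotherapy. The size is 5.0 points per such patient at n=20 and 4.2 at n=24, assuming the patient would otherwise be a non-responder and attends the visit that maps to Week 26. The number of switchers is not in the documents; if it is zero there is no effect.

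Two stronger readings are not supported. One is that the reported rate will be inflated by 10 points or more: that needs several switchers, and any such count is an assumption. The other is that a development decision would change: the documents give no go/no-go threshold. The change is worth making because it is cheap and concerns the primary result; confidence is medium.

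**What to change.** Add a rule to SAP 4.7.1, 4.7.2 and 4.7.4 for the binary endpoints. Keep in the denominator, and score as a non-responder at all later visits, any patient who before the Week 26 assessment:
- discontinues study drug for new anti-AD treatment;
- starts systemic AD therapy or phototherapy after first dose; or
- starts topical AD therapy after stopping study drug for any reason.

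A non-response score has no meaning for percent change. For percent change in EASI and PP-NRS (SAP 4.7.1, 4.7.3), set values after the switch to missing. For EASI do this before LOCF, so that only pre-switch values are carried forward. Report the as-observed result as a sensitivity analysis.

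Build the flag mainly from the discontinuation reason already tabulated under SAP 4.2, supported by the medication and non-medication therapy data under 4.5 and 4.6. SAP 4.5 does not say that indication is recorded, so identification outside the discontinuation reason may be incomplete. The rule does not restore patients who stop early for other reasons; that is a general missing-data question.

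Cost: SAP wording and one derived flag, with no protocol amendment. The rule is conservative for a patient who would have responded anyway, by up to 5.0 points per patient at n=20 or 4.2 at n=24, which the as-observed analysis will show. The study is open-label and, per Protocol 5.6, already under way, so the SAP change should be dated and justified before database lock.
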